13.1.2 Efficacy, Safety and Other Variables

13.1.2.1 Efficacy Variables

The clinical benefit of CHIMAERA™ will be assessed by the percentage of patients in which bone union has been achieved within 12 months from the nail implant.

The clinical benefit analysis will be performed in those patients who meet the following criteria:

- Patient has achieved bone union at the 12 months follow-up visit and this is the only evaluation available.
- Patient has achieved bone union at first follow-up this being the only evaluation available.
- Patient has both bone union evaluations completed (first follow up visit and last follow up visit) and achieved bony union at the end of the follow-up period. (considered a responder)
- Patient underwent reoperation but the reason for this was secondary dynamization.
- Patient with fractures on the upper limbs not caused by the CHIMAERA™ (e.g. simply stumbled or had a car accident)
- Patient underwent reoperation after first bone union evaluation.
- Patient who has not suffered contralateral leg fracture.
- Patient in whom no refracture occurred where the nail was applied.

A double evaluation will be required (observer 1 and observer 2). Only if both evaluations are positive, the treatment goal will be considered achieved.

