8 STUDY DESIGN

The CHIMAERA study is designed as a retrospective, non-interventional, multicenter, PMCF study intended to evaluate both clinical benefit and safety profile of CHIMAERA™ device in adult patients according to the manufacturer IFU in routine clinical practice.

The study has been designed to retrospectively analyze the patient's medical records of patients who underwent a surgical implantation of CHIMAERA™ part of the site routine clinical practice. Data collection will be carried out during the study observation period, from the surgery until the last follow-up visit within 12-months after nail implant. Information will be collected from the different evaluations made by the subject in accordance with routine clinical practice, including the day of surgery, the hospital discharge, the bone consolidation assessment (1st follow up visit), the second follow up visit (2nd follow up visit), the last follow-up visit (3rd follow up visit), and additional surgeries if it occurred within 12 months after nail implant. Surgeons belonging to the 2 study sites who will participate in the study must have full awareness of orthopedic fixation procedures and should be familiar with the devices, instruments and surgical procedure, including the application and removal. After reviewing the selection criteria and confirming patient eligibility, demographic, and clinical and safety information from the time of surgery until the last follow-up visit will be collected from medical records.

[figure not shown]
To ensure the observational nature of the study, study data (demographics, clinical performance and safety data) will be collected from data already recorded in the medical records according to routine clinical practice. No diagnostic or therapeutic intervention outside of routine clinical practice will be applied.

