13 ANALYSIS POPULATION

- **The full analysis set (FAS) population** consists of all patients included in the study after selection criteria review, patients who meet all selection criteria. The CRF contains the screening criteria information in the form of a binary variable (Yes/No) for each item described. The full analysis set will be used for all descriptive analysis.
- **The clinical benefit population** consists of patients who have available data that allow the primary efficacy endpoint assessment. The clinical benefit population will be used for primary objective (see primary objective section).
- **The safety population** includes all adult patients in whom CHIMAERA™ has been used. It includes all patients who have undergone an intramedullary nailing technique with the CHIMAERA™ medical device. The safety analysis will be performed in the “safety population” which includes all patients who have undergone an intramedullary nailing technique with the CHIMAERA™ medical device.

A list of patients belonging to each of the populations will be sent to the sponsor for confirmation prior to analysis.

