21 THIRD FOLLOW UP VISIT (12 MONTHS)

This analysis will be performed on FAS population.

The descriptive statistic (Mean, SD, Median, Q₁, Q₃, Min, Max) will be shown for the following continuous variable:

- Time from surgery to third follow up visit (days) (calculated as Date of third follow up minus date of surgery)

The categorical variable to be described is, N and (%):

- Time from surgery to third follow up visit (months) within the time windows estimated in the protocol (9-15 months)? (Yes / No)

The categorical variables to be described are, N and (%):

- Was the patient examined on an outpatient basis or contacted by telephone because he was unable to reach your hospital? (Outpatient visit / Telephone contact)
- Have the medications the patient takes regularly changed? YES / NO, If "YES", type and dosage will be shown.
- Did the patient refer any info related to pain at the site of nail application? YES / Data not available), If "YES" will be described:
 - No pain
 - Pain
- During the year did the patient come back to work? (YES / NO / At time of surgery the patient didn't work at all / Data not available)
- Are follow up fluoroscopies (AP + ML) or, preferably, RX (AP + ML) available? YES / NO

The descriptive statistic (Mean, SD, Median, Q₁, Q₃, Min, Max) will be shown for the following continuous variables:

- Xap (mm)
- Dap (mm)
- Xlat (mm)
- Dlat (mm)
- TAD (mm)

The categorical variables to be described are, N and (%):

- Observer 1: According to medical opinion, is/are the fracture/s treated with Chimaera nail consolidated? YES / NO, If "NO", motivate will be described
- Observer 2: According to medical opinion, is/are the fracture/s treated with Chimaera nail consolidated? YES / NO, If "NO", motivate will be described.

- Number of patients in which consolidation has been achieved according to the two observers.

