23 PRIMARY OBJECTIVE

Primary objective: the primary objective of this study is to evaluate the clinical benefit of the long variant of the CHIMAERA™ used in adult patients according to the IFU in routine clinical practice from the time of surgery within 12 months follow-up after nail implant.

This analysis will be performed on the clinical benefit population.

The clinical benefit analysis will be performed in those patients who meet the following criteria:

- Patient has achieved bone union at the 12 months follow-up visit and this is the only evaluation available.
- Patient has achieved bone union at first follow-up this being the only evaluation available.
- Patient has both bone union evaluations completed (first follow up visit and last follow up visit) and achieved bony union at the end of the follow-up period. (considered a responder)
- Patient underwent reoperation but the reason for this was secondary dynamization. *If it will be indicated 'secondary dynamization' in ADDITIONAL SURGERY the patient will be included in this analyses (all other no).*
- Patient with fractures on the upper limbs not caused by the CHIMAERATM (e.g. simply stumbled or had a car accident) . *ADVERSE EVENTS section, answer "Unanticipated/Other adverse event (specify below)" specifying that an upper limb fractures occurred, but is "not related" to Chimaera (question "According to medical opinion, is the Adverse Event related to Chimaera?") (if it is collected any upper limbs fractures "related" to Chimaera in the question "unanticipated/Other adverse event", the patient will not be included in the analyses (not belong to clinical benefit population).*
- Patient underwent reoperation after first bone union evaluation. FU visit 1 or 3: the observer 1 and observer 2 certify that the bone union has been assessed. *Those patients in which the answers where "YES" and subsequently underwent a reoperation in ADDITIONAL SURGERY will be included (excluded the option "secondary dynamization").*
- Patient who has not suffered contralateral leg fracture. *EXCLUSION CRITERIA "Has the patient been diagnosed with bilateral proximal femur fractures? YES / NO" should be "NO".*
- Patient in whom no refraction occurred where the nail was applied. *This is to be found in ADVERSE EVENT (if it is marked 'bone fracture' the patient will not be included in this analyses).*

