The categorical variable to be described is, N and (%) and Clopper-Pearson confidence intervals will be shown at 95.0% as well:

- Number of patients that reached consolidation according to the two observer's opinion in at least one visit (visit 1 or visit 3). Only if both evaluations are positive in each visit, the treatment goal will be considered achieved.

The descriptive statistic (Mean, SD, Median, Q₁, Q₃, Min, Max) will be shown for the following continuous variable:

- Time to consolidation from surgery (months), considered at the first visit in which the answer is “Yes” in “According to medical opinion, is/are the fracture/s treated with Chimaera nail consolidated?” variables in both observers. Calculated as date of first date of consolidation minus date of surgery.

A list with consolidation variables will be shown.

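### SAP 23 gives inconsistent responder rules for the primary union rate, can drop non-united patients from the denominator, and applies no 12-month date test

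*SAP*

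**What the plan says.** - **Endpoint.** Protocol 13.1.2.1 takes the percentage of patients in whom "bone union has been achieved within 12 months from the nail implant". Protocol 8.1 and SAP 8 describe data collection as running "from the surgery until the last follow-up visit within 12-months after nail implant".
- **Counting rule.** SAP 23 reports N, % and a Clopper-Pearson interval for patients consolidated in both observers' "opinion in at least one visit (visit 1 or visit 3". The next sentence requires both evaluations to be positive *in each visit*. Neither sentence has a date condition.
- **Criteria list.** Protocol 13.1.2.1 and SAP 23 list eight criteria for the patients to be analysed. The first is union at the 12-month visit as the only evaluation. The second is union at the first follow-up as the only evaluation. The third is both evaluations done and "achieved bony union at the end of the follow-up period. (considered a responder".
- **Population.** SAP 13 says the clinical benefit population "consists of patients who have available data that allow the primary efficacy endpoint assessment", and points to the primary objective section.
- **Visit timing.** SAP 21 tabulates whether visit 3 fell "within the time windows estimated in the protocol (9-15 months". This is a yes/no description and is not used to select readings.
- **Re-reading.** Protocol 11.2 asks for a union reading at the last visit only if union had not been achieved, as far as its wording can be followed. SAP 21 lists the visit 3 reading without that condition. SAP 20 has no union reading at visit 2.

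**The concern.** The primary rate has one numerator and one denominator, and SAP 23 describes each in more than one way.

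First, *at least one visit* and *end of follow-up* give different answers for a patient read as united early and not united later, and no order of precedence is stated.

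Second, the first three criteria introduce the patients to be analysed, yet each of them contains the outcome. Used as a gate, they let patients in because they united. A patient with a negative reading then has no matching criterion and can disappear from the denominator instead of counting as a non-responder.

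Third, nothing in the counting rule checks that a positive reading was dated within 12 months.

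The rate is the study's main result and is meant to help confirm the benefit/risk ratio (Protocol 6.2). Two analysts who both follow SAP 23 could report different figures from the same data.

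**Working it through.** **Inputs.** N = 44 planned (Protocol 13.2, SAP 9); Clopper-Pearson 95% intervals (SAP 14 and 23); visit 3 window 9-15 months (SAP 21); endpoint limit 12 months (Protocol 13.1.2.1). The plan states no number of discordant, non-united or late-read patients, so there is no figure of its own to reproduce here. N is taken as given.

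**Step 1: apply each rule to each pattern of readings** (+ means both observers positive).

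| Visit 1 | Visit 3 | Counting rule | Criteria 1-3 as definition of response | Criteria 1-3 as entry gate |
|---|---|---|---|---|
| + | not read | united | united | admitted |
| not read | + | united | united | admitted |
| - | + | united | responder | admitted |
| + | + | united | responder | admitted |
| + | - | **united** | **non-responder** | **excluded** |
| - | - | not united | non-responder | **excluded** |
| - | not read | not united | non-responder | **excluded** |
| not read | - | not united | non-responder | **excluded** |

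The first conflict is confined to the + / - row. The gate reading affects all four of the last rows.

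**Step 2: size per patient.** 1/44 = 2.27 percentage points; 2/44 = 4.55 points, close to the 5% imprecision used for the sample size.

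**Step 3: intervals.** Lower limit = Beta quantile(0.025; x, n-x+1); upper limit = Beta quantile(0.975; x+1, n-x). For x = n the lower limit is 0.025^(1/n) and the upper limit is 100%. Illustration, with all other patients united:

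- None affected: 44/44 = 100% (92.0-100).
- One patient not united at the last reading, kept as non-responder: 43/44 = 97.7% (88.0-99.9). Same patient dropped by the gate: 43/43 = 100% (91.8-100).
- Two such patients, kept: 42/44 = 95.5% (84.5-99.4). Dropped: 42/42 = 100% (91.6-100).

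If the affected patient has the + / - pattern, the counting rule gives 44/44. That one patient can therefore produce 44/44, 43/44 or 43/43.

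**Step 4: dates.** The visit 3 window extends 15 - 12 = 3 months past the endpoint limit. A union first read in those months meets the counting rule as written. Whether such a reading exists in the database depends on whether collection really stops at month 12, as Protocol 8.1 and SAP 8 say.

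**The case against.** Much of the case on the other side stands.

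- **Collection limit.** SAP 23 restates 12 months in its objective, its first criterion names the 12-month visit, and the study design sections confine collection to 12 months. Scoring a 12-month endpoint at a nominal visit with a window is ordinary practice. The window is attributed to the protocol and may stand in the schematic, which is not shown. A reader might infer that unions at months 13-15 will be counted, or that half of the unions first read at visit 3 are late because half of the window lies after month 12. The documents support neither: the first requires readings outside the stated collection period, and the second requires visit dates spread evenly over the window.
- **Visibility.** SAP 23 also asks for time to consolidation with its maximum and a list of consolidation variables, so a late reading would not be hidden. The label on the rate would still not match it.
- **Rarity of the discordant pattern.** Under Protocol 11.2 a union seen at visit 1 is apparently not re-read, and the last criterion removes refractures at the nail. A reader might point to the sixth criterion, under which patients read as united who "subsequently underwent a reoperation in ADDITIONAL SURGERY will be included", as proof that discordant patients exist. It is not: a reoperation is not a negative union reading. Its tension with the fourth criterion, "the patient will be included in this analyses (all other no", is a separate drafting matter.
- **Population definition.** SAP 13 cannot simply be set against the list, because it refers to SAP 23, where the annotations to the list do decide who belongs to the population.

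This does not remove the two responder rules, the outcome wording inside the entry list, or the missing date test.

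**Conclusion.** The concern holds as an inconsistency in the definition of the primary rate. The denominator is its most important part: with the first three criteria read as entry conditions, patients who did not unite can leave the analysis and the rate is pushed towards 100%.

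A reader might infer that the rate is 100% by construction. The text does not go that far. SAP 13 defines the population by available data, and the list does not say how its eight items combine. The first two cannot both be met, since each requires its reading to be the only one.

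The number of patients affected is unknown and may be nil. Each one reclassified moves the rate by 2.3 points if 44 are analysed. The study is descriptive with no success threshold, so no pass/fail decision depends on this. The change is still worth making before analysis.

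**What to change.** 1. In SAP 23, reword the first three criteria so that they define response and not entry. As far as those three are concerned, every patient with a union reading stays in the denominator, and those not united are non-responders. The protocol carries the same list, so the SAP should say that this is how it reads it.
2. Use one counting rule: a responder has both observers positive at the same visit, at the last available union reading. A positive visit 1 stands if union was not re-read. Replace *in each visit* with *at the same visit*.
3. Label the rate *by the 12-month visit (9-15 months)*. Beside it, from dates already collected, show how many responders had their first positive reading dated 12 months or less from implant and how many were first read as united later. In that breakdown, list patients without a reading near month 12 separately and do not score them as failures of the 12-month limit.

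**Cost.** SAP wording and one extra line of output, with no new data. The reported rate may be slightly lower. A patient whose only reading is an early negative counts as a non-responder in the main rate although later union is possible; the separate listing shows how many there are.

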24 SECONDARY OBJECTIVES

Secondary objective: to evaluate the safety profile of the long variant of the CHIMAERA™ used in adult patients according to the manufacturer IFU in routine clinical practice from the time of surgery until 6 months follow-up after nail implant.

The safety analysis will be performed in the safety population.

24.1 ADDITIONAL SURGERY

24.1.1 ADDITIONAL SURGERY DESCRIPTION

The categorical variables to be described are, N and (%) and Clopper-Pearson confidence intervals will be shown at 95.0% as well:

- Patients with at least one additional surgery
- Number of additional surgeries per patient
- What is the reason of additional surgery? (Adverse Event / Device Deficiency / Secondary dynamization / Other (a list will be shown))
- Number of patients with at least one additional surgery which reason was Adverse Event
- Number of patients with at least one additional surgery which reason was Device Deficiency
- Number of patients with at least one additional surgery which reason was Adverse Secondary dynamization
- Number of patients with at least one additional surgery which occurs in surgery visit
- Number of patients with at least one additional surgery which occurs in discharge visit
- Number of patients with at least one additional surgery which occurs in follow up visit 1
- Number of patients with at least one additional surgery which occurs in follow up visit 2
- Number of patients with at least one additional surgery which occurs in follow up visit 3

For the total number of additional surgeries, the descriptive statistic (Mean, SD, Median, Q₁, Q₃, Min, Max) will be shown for the following continuous variable:

- Duration of the surgery (skin to skin) (minutes)

For the total number of additional surgeries, the categorical variables to be described are, N and (%):

- Has the patient been transfused? YES / NO, If "YES", descriptive statistic (Mean, SD, Median, Q₁, Q₃, Min, Max) of the number of used blood bags will be shown

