7.2 Secondary Objectives

The secondary objective of this study is to evaluate the safety profile of the long variant of the CHIMAERA™ used in adult patients according to the manufacturer IFU in routine clinical practice since nail application until 6 months after nail implant.

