13.1.2.2 Safety Variables

The safety profile of CHIMAERA™ will be assessed through the percentage of patients that required a reoperation (i.e., additional surgery) caused by at least one of the following safety events:

- Expected or unexpected adverse effect potentially or certainly related to the CHIMAERA™ (Adverse Device Effects (ADEs)/Serious Adverse Device Effects (SADEs)) since the nail application until 6 months follow-up after nail implant.
- Medical Device Deficiency (MDDs) (i.e., breaking, loosening, or bending of the nail or of the screws) that caused an effect on the patient since the nail application until 6 months follow-up after nail implant.

All the reoperations that have occurred are considered but also those that have not occurred but that could have occurred (e.g., a patient who had a cut out but for any reasons has not been operated). It should be considered also all ADE/SADE/MDD that could have caused an additional operation.

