13.1.3.2 Evaluation of Safety

The evaluation of safety will be performed through the analysis of the secondary objective of the study: to evaluate the safety profile of the long variant of the CHIMAERA™ used in adult patients according to the manufacturer IFU in routine clinical practice from the time of surgery until 6 months follow-up after nail implant.

The safety analysis will be performed in the “safety population” which includes all patients who have undergone an intramedullary nailing technique with the CHIMAERA™ medical device.

The number and percentage of patients that required a reoperation due to at least one ADE/SADE/MDD will be calculated with a 95% confidence interval (CI). An analysis will be carried out according to degree of severity, seriousness, and relationship with the medical device.

All the reoperations that have occurred are considered but also those that have not occurred but that could have occurred (e.g., a patient who had a cut out but for any reasons has not been operated). It should be considered also all ADE/SADE/MDD that could have caused an additional operation. Therefore, the number and percentage of patients that hypothetically would have caused a reoperation due to at least one safety event will be described and calculated with a 95% CI.

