20 SECOND FOLLOW UP VISIT (6 MONTHS)

This analysis will be performed on FAS population.

The descriptive statistic (Mean, SD, Median, Q₁, Q₃, Min, Max) will be shown for the following continuous variable:

- Time from surgery to second follow up visit (months) (calculated as Date of second follow up minus date of surgery)

The categorical variable to be described is, N and (%):

- Time from surgery to second follow up visit (months) within the time windows estimated in the protocol (3-9 months)? (Yes / No)

The categorical variables to be described are, N and (%):

- Was the patient examined on an outpatient basis or contacted by telephone because he was unable to reach your hospital? (Outpatient visit / Telephone contact)
- Have the medications the patient takes regularly changed? YES / NO, If "YES", type and dosage will be shown.
- Did the patient refer any info related to pain at the site of nail application? YES / Data not available), If "YES" will be described:
 - No pain
 - Pain

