24.2 ADVERSE EVENTS

The categorical variables to be described are, N and (%) and Clopper-Pearson confidence intervals will be shown at 95.0% as well:

- Patients with at least one adverse event
- Patients with at least one serious adverse event
- Patients with at least one related adverse event (considering related as Possible, Probable and Casual relationship)
- Patients with at least one adverse event which require additional surgery

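### SAP section 24 specifies no output for the protocol's only secondary endpoint, device-related reoperation up to 6 months, actual or hypothetical

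*SAP*

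**What the plan says.** **Protocol.** Section 13.1.2.2 defines the safety endpoint as the percentage of patients with a reoperation caused by one of two kinds of event. The first is "Expected or unexpected adverse effect potentially or certainly related to the CHIMAERA™". The second is a device deficiency, limited there to one that had an effect on the patient. Both carry the 6-month limit. The section adds that reoperations that could have occurred but did not are also considered.

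Section 13.1.3.2 sets the analysis as two patient counts, each with its percentage. For actual reoperations it reads: "patients that required a reoperation due to at least one ADE/SADE/MDD will be calculated with a 95% confidence interval". For those that did not take place it reads: "patients that hypothetically would have caused a reoperation due to at least one safety event will be described and calculated with a 95% CI". The horizon in section 7.2 is "since nail application until 6 months after nail implant".

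**SAP.** Section 24 restates the objective as "from the time of surgery until 6 months follow-up after nail implant" and assigns it to the safety population. The outputs nearest to the endpoint are:

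- 24.1.1: "Number of patients with at least one additional surgery which reason was Adverse Event", a separate row of the same form for device deficiency, and rows by visit from surgery to follow-up visit 3. All are patient counts with Clopper-Pearson intervals.
- 24.2: "Patients with at least one adverse event which require additional surgery", also with an interval. A separate row counts patients with any related adverse event, where related means possible, probable or causal.
- The subsection on additional surgery for adverse events, and 24.3.3 for device deficiencies: whether an event that was not operated could have led to surgery, tabulated per event as N and %.

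**The concern.** The SAP is where the protocol's endpoint should become a defined table row. Here the objective sentence is carried over, but the conditions that define the endpoint (relatedness, the 6-month limit, the combination of causes, the patient as unit) do not reach the outputs.

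The study is meant to support the benefit/risk evaluation of the device and its CE mark. A reader of the report would take the reoperation rows as the safety result, yet those rows can include surgeries for unrelated events and surgeries after 6 months. If the endpoint is instead derived after the data are seen, several choices are made at that point: the date basis, the roll-up from events to patients, and whether hypothetical reoperations count.

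**Working it through.** The documents give no expected count or precision for this endpoint, so there is no planned figure to reproduce. The check sets each element of the protocol definition against the rows of SAP 24.

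| Protocol element | In SAP 24 |
|---|---|
| Reoperation due to a device-related effect | 24.1.1 and 24.2 count surgery for adverse events of any causality. The related category is never crossed with surgery. |
| Or a device deficiency that affected the patient | Separate row in 24.1.1, without the patient-effect condition |
| Either cause, per patient, with 95% CI | No row |
| Up to 6 months | In the objective sentence only |
| Hypothetical reoperation, per patient, with 95% CI | Per adverse event and per deficiency; no patient count, no CI |

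**Relatedness.** Unrelated events are in the data. SAP 24.2.2 (related adverse events) tabulates a not-related category, and SAP 23 uses an upper-limb fracture unrelated to the nail as an example of a recorded adverse event. If such an event were marked as requiring surgery, the row in 24.2 would count it.

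**Time.** Protocol 11.2 collects reoperations to 12 months, and device effects and deficiencies to the last follow-up visit. The by-visit rows in 24.1.1 cannot supply a 6-month cut. Visit 2 is assessed "within the time windows estimated in the protocol (3-9 months"), so it straddles month 6, and the rows are not split by reason. The visit 3 row (window 9-15 months in SAP 21) lies wholly beyond 6 months, although it sits under a 6-month objective.

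**Combined row.** Assume 2 patients with surgery for a related adverse event and 1 with surgery for a deficiency. The separate rows would show 2/44 = 4.5% (0.6-15.5) and 1/44 = 2.3% (0.1-12.0). With no overlap the composite is 3/44 = 6.8% (1.4-18.7). If the deficiency patient is one of the other two, it is 2/44 = 4.5% (0.6-15.5). The separate rows do not show which holds, and without overlap the composite interval appears nowhere.

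**Hypothetical item.** The question in the adverse-event subsection is worded for the device deficiency and not for the adverse event.

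**Size.** Inputs: N = 44 (Protocol 13.2), Clopper-Pearson 95% (SAP 14), and the literature average of 5.9% with range 0.0%-27.5% (Protocol 6.1, SAP 2.1). The limits for x of n are the 2.5% quantile of Beta(x, n − x + 1) and the 97.5% quantile of Beta(x + 1, n − x).

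- One patient: 1/44 = 2.27 points; 2.27/5.9 = 0.39 of the literature average.
- Patients implied by that average: 44 × 0.059 = 2.6. Over the range: 44 × 0 = 0 to 44 × 0.275 = 12.1.
- Assumed 3 endpoint patients: 3/44 = 6.8% (1.4-18.7).
- The same 3 plus one patient with an unrelated or late surgery: 4/44 = 9.1% (2.5-21.7).
- Assumed 2 endpoint patients plus three such patients: 2/44 = 4.5% (0.6-15.5) becomes 5/44 = 11.4% (3.8-24.6).

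The counts are assumptions, chosen near the 2.6 patients that the literature average implies.

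**The case against.** The best defence is that the protocol already specifies the analysis, that SAP 24 restates the horizon and the population, and that the listings of surgeries, adverse events and deficiencies would let an analyst build the endpoint. That is largely true. A reader might infer that the endpoint is lost or cannot be computed. The documents do not support this: reoperation date and reason (Protocol 11.2) and adverse event dates and causality (Protocol 12.2) are collected. But a listing is not a specified estimate with an interval. Nor can the objective sentence be read as limiting every row to 6 months, because the visit 3 row beneath it contradicts that.

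It could also be said that separate rows suffice unless one patient had surgeries for different reasons. They do not, because Protocol 13.1.3.2 asks for the interval of the composite whether or not reasons overlap.

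Three further inferences go too far:

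- That the gap could reverse the study's conclusion. The study is single-arm and descriptive with no threshold, and the illustrative intervals overlap widely.
- That the 6-month limit really means visit 2 with its 3-9 month window. The sections that mention follow-up also say after nail implant, and Protocol 7.2 and SAP 7 state a calendar limit.
- That a corrected row would be directly comparable with 5.9%. That figure is given for adverse device effects only, without a follow-up time, whereas the endpoint also includes device deficiencies.

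The device-deficiency wording in the adverse-event item may be a copying slip. The eCRF is a separate document and was not available to check.

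**Conclusion.** The point holds and should be fixed. As written, SAP 24 outputs neither of the two patient-level figures that Protocol 13.1.3.2 requires for the only secondary endpoint, and its closest rows measure something wider. The textual finding rests on no assumption; only the illustrative counts do. Each misclassified patient moves the estimate by 2.3 points at the planned maximum of 44, and by more if fewer patients are included.

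Two matters within the protocol also need settling. Section 13.1.2.2 counts actual and hypothetical reoperations together, while 13.1.3.2 reports the hypothetical ones as a separate figure, so it is unclear which is the endpoint. Section 13.1.2.2 also limits deficiencies to those that affected the patient, and 13.1.3.2 does not repeat this.

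**What to change.** Add to SAP 24, in the safety population, patient-level N, % and Clopper-Pearson 95% CI for:

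1. at least one additional surgery caused by an adverse event with possible, probable or causal relationship, or by a device deficiency that affected the patient (stating that a reoperation itself counts as an effect);
2. no such surgery, but at least one related adverse event, or one deficiency meeting the patient-effect condition, flagged as one that could have led to additional surgery;
3. either of these.

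State which row is the endpoint, and reconcile Protocol 13.1.2.2 and 13.1.3.2 on the patient-effect condition. Apply the limit by date at 6 calendar months after implant (Protocol 7.2, SAP 7), on the date of the safety event, which is where Protocol 13.1.2.2 places it. Say how a later surgery for an earlier event is counted, and show later surgeries on a separate descriptive line. If 5.9% is used for comparison, also show the component for adverse device effects alone.

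Before database lock, check the eCRF wording behind the hypothetical item for adverse events, and confirm that a date is captured for device deficiencies, since the documents list none.

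The cost is SAP wording and a few derived rows, from data that are largely collected already.
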